### **7.4. Vital Signs**

The vital signs pulse, temperature, and the mean (from triplicate measurements) sitting blood pressure will be assessed during screening; on Treatment Phase Day 0 (i.e. Baseline), Treatment Phase Day 7, and Treatment Phase Day 28 of each treatment phase; and at a patient's early termination visit, if applicable.

The number and percent of patients with any post-baseline pulse rate or mean blood pressure of potential clinical interest (including unscheduled and early termination assessments) will be summarized. Readings of potential clinical interest will be determined using the following criteria:

- Pulse rate either  $< 50$  bpm, or  $> 100$  bpm, or a change of  $\geq 15$  bpm;
- Systolic blood pressure either  $\leq 90$  mmHg, or  $\geq 160$  mmHg, or a change of  $\geq 20$  mmHg;
- Diastolic blood pressure either  $\leq 50$  mmHg, or  $\geq 100$  mmHg, or a change of  $\geq 10$  mmHg.

### **7.5. Electrocardiogram Summaries**

Single 12-lead electrocardiograms (ECGs) will be assessed during screening; on Treatment Phase Day 0 (i.e. Baseline), Treatment Phase Day 7, and Treatment Phase Day 28 of each treatment phase; and at a patient's early termination visit, if applicable. Two-hour post-dose ECG assessments will also be made at Baseline of each treatment phase.

The number and percent of patients with any post-baseline Fridericia-corrected QT values of potential clinical interest (including unscheduled and early termination assessments) will be summarized. QTcF values of potential clinical interest will be determined using the following criteria:

- QTcF  $\geq$  480 msec, or  $\geq$  500 msec, or  $\geq$  550 msec
- Change from baseline in QTcF  $\geq$  30 msec, or  $\geq$  60 msec.

## 7.6. Columbia Suicide Severity Rating Scale

The Columbia-Suicide Severity Rating Scale (C-SSRS) will be listed by patient and visit.

Only patients that show suicidal ideation and/or behavior will be displayed (i.e. if a patient's answers are all 'no' for the CSSRS, that patient will not be listed). However, if a patient reported any suicidal ideation and/or behavior, all of their ideation and behavior will be displayed, even if not positive.

## 8. EXPLORATORY ANALYSES

Exploratory endpoints will be summarized separately as pharmacodynamic (i.e. AG, UAG, AG/UAG ratio), anthropometric (i.e. body weight, percentage fat mass, BMI, waist circumference), and exploratory blood chemistry (i.e. low-density lipoproteins, total cholesterol, and blood glucose) endpoints.

All exploratory endpoint analyses will be performed using the Evaluable Population, using the same methods used for the primary efficacy endpoint. Descriptive statistics for the value and change from baseline will be tabulated for each time point.

In addition, plots of the individual AG and UAG levels as well as their mean levels by treatment will be plotted over time.

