A clinical study conducted in 3 PWS expert centers in the Netherlands and France compared AG and UAG levels, and the AG/UAG ratio, in patients with PWS (n=138, 0.2 to 29.4 years), obese subjects (n=50; 4.3 to 16.9 years), and healthy control subjects (n=39, 0.8 to 28.6 years). Concentrations of AG were higher in PWS compared to healthy control subjects, while UAG was similar to that of control subjects. Both AG and UAG were significantly lower in the obese group than for PWS and control subjects. These differences in AG and UAG concentrations were reflected in elevated AG/UAG ratios in patients with PWS who exhibited weight gain and/or hyperphagia; while those without weight gain or hyperphagia had ratios comparable to those of age-matched control subjects. The authors proposed that the switch to excessive weight gain in PWS appears to coincide with an increase in the AG/UAG ratio, even preceding hyperphagia (Kuppens *et al.* 2015).

These AG and UAG data are overall consistent with a multiple ascending dose study of GLWL-01 in overweight and obese adult patients with type 2 diabetes (n=38), which showed a decrease in AG without weight loss, and low UAG concentrations. Since hyperphagia behaviors may be linked to elevated AG concentrations in patients with PWS, GLWL-01 may lower elevated AG concentrations and thus reduce hyperphagia behaviors.

GLWL-01 is a small molecule inhibitor of GOAT, which is superficially expressed primarily in the stomach and pancreas of humans and rats. GLWL-01 is the first GOAT inhibitor being clinically evaluated for the treatment of PWS. Inhibition of GOAT is expected to lower AG and raise UAG plasma levels.

GLWL-01 is a potent inhibitor of human GOAT with an IC_{50} of 192 nM in a primary enzyme assay and of 8.20 nM in a cell-based assay. In the nonclinical pharmacology studies, GLWL-01 demonstrated dose-dependent reduction in AG concentrations and increases in UAG concentrations (GLWL-01 [2017](#)).

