10.1. Sample Size Determination

Approximately 34 patients will be randomized to 1 of 2 treatment sequences (GLWL-01/placebo or placebo/GLWL-01) in a 1:1 ratio. Thirty-four patients will provide approximately 80% power to detect an effect size of 0.75 for the HQ-CT total score using a 2-sided exact paired t-test with an $\alpha=0.05$, assuming 10% drop out.

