10.3. Statistical Analyses

10.3.1. General Statistical Considerations

Statistical analysis of this study will be the responsibility of GLWL Research Inc. or its designee.

Efficacy analyses will be conducted on the randomized analysis set. This set includes all data from all randomized patients receiving at least 1 dose of double-blind study drug. Patients will be included in the analysis if they have a postbaseline measurement for the parameter being analyzed. Safety analyses will be conducted on the randomized analysis set. Patients will be analyzed according to the study drug they actually received.

Data will be presented using summary tables by treatment, unless otherwise specified.

Continuous data will be summarized using the mean, standard deviation, median (for selected variables), minimum, and maximum. Categorical data will be summarized as frequency counts and percentages. Figures may be used to support the presentation of selected data.

All tests of treatment effects will be conducted at a 2-sided alpha level of 0.05, unless otherwise stated.

Baseline values will be defined as the last available value prior to receiving double-blind study drug for each double-blind treatment phase.

For the purposes of follow-up analyses, the first 2 weeks of the washout period will be the follow-up for the Treatment Period 1 double-blind treatment phase and the Follow-up Period will be the follow-up for the Treatment Period 2 double-blind treatment phase.

Details related to handling of missing data will be described in the statistical analysis plan (SAP).

Any change to the data analysis methods described in the protocol will require an amendment only if it changes a principal feature of the protocol. Any other change to the data analysis

methods described in the protocol, and the justification for making the change, will be described in the SAP and/or in the clinical study report (CSR).

Additional exploratory analyses of the data will be conducted as deemed appropriate.

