## **2.9. Changes to the Planned Analyses**

Note that what is now called the **Evaluable Population** was called the **Randomized Population** in the protocol.

Blood glucose was added to the list of exploratory endpoints.

The determination of a treatment-emergent adverse event has been changed from that in the protocol, because the way adverse events are actually being captured is not as was anticipated. Specifically, an ongoing adverse event that worsens during the study will be captured as a new adverse event, so that adverse events that start during one period of the trial and get worse during a different period of the trial (which defines treatment-emergent) will have separate records that will be summarized separately.

The statistical analyses will be performed as 1-sided tests rather than 2-sided tests as originally planned, because enrollment was stopped prior to obtaining the intended 34 patients. With the anticipated 19 patients, there is at least 70% power for the primary treatment comparison, which is still considered acceptable for a proof of concept trial.

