## **6. EFFICACY ANALYSES**

Efficacy analyses for this study will be based on the findings from two instruments. First, the HQ-CT is a validated tool developed specifically for PWS to capture observations of problematic behaviors related to food. It consists of 9 items, with a 2-week recall period. The scale provides a composite value from 9 questions, each rated on a scale of 0 to 4 units (total range of score of 0 to 36; Fehnel et al. 2015).

Second, the CGIC is a single-item question rated on a 0 to 7 scale directed at the caregiver asking for an assessment of the overall improvement of patients with PWS.

Both of these assessments will be collected longitudinally during the study.

All efficacy analyses will be performed using the Evaluable Population. The method of analysis or statistical technique employed to address missing data will be described separately for each variable. Presentations of efficacy will include the number of patients with data at each time point plus related statistics derived from the analysis.

All statistical tests will be 1-sided.

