## **7. SAFETY ANALYSES**

All summaries of safety, including the extent of exposure to study medication, will be performed using the Evaluable Population. No statistical analyses are planned on safety endpoints.

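### SAP 8 carries the switch to 1-sided tests over to all ten exploratory endpoints with no direction or alpha stated, although the only reason given concerns power for the primary HQ-CT comparison

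*SAP*

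**What the plan says.** Protocol 10.3.1 sets the general rule: "All tests of treatment effects will be conducted at a 2-sided alpha level of 0.05, unless otherwise stated". Protocol 10.3.3.3 analyses the exploratory endpoints with the primary methodology, so under the protocol they are tested 2-sided.

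SAP 2.9 changes the statistical analyses from 2-sided to 1-sided because enrolment stopped short of 34, and adds: "With the anticipated 19 patients, there is at least 70% power for the primary treatment comparison". SAP 6 repeats the change without exception: "All statistical tests will be 1-sided". Neither section states the 1-sided alpha.

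SAP 8 covers AG, UAG, AG/UAG ratio, body weight, percentage fat mass, BMI, waist circumference, LDL, total cholesterol and blood glucose. For these it says: "All exploratory endpoint analyses will be performed using the Evaluable Population, using the same methods used for the primary efficacy endpoint". It gives no direction for any of them and does not exempt them from the 1-sided rule.

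On expected direction, the primary objective in SAP Table 1 is a reduction in hyperphagia behaviours, so HQ-CT should fall. The exploratory objective in the same table is to evaluate an effect, with no direction. Protocol 3.2 says of the mechanism: "Inhibition of GOAT is expected to lower AG and raise UAG plasma levels". For safety data, SAP 7 says: "No statistical analyses are planned on safety endpoints".

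**The concern.** The reason given for 1-sided testing does not reach the exploratory endpoints. The documents make no power claim for any of them, and early stopping does not turn a question about an effect in either direction into a question about one direction.

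Two groups of endpoints are affected. UAG is a mechanism measure whose expected change is opposite in sign to that of HQ-CT. Weight, body composition, lipids and glucose could move either way on drug. Because SAP 7 drops formal safety comparisons, the SAP 8 models are the only planned formal treatment comparison of weight, glucose and lipids. A 1-sided test for a decrease cannot separate no effect from worsening.

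The missing direction matters on either reading. Carried over from HQ-CT, it is wrong for UAG and one-eyed for the metabolic measures. Left to the analyst, it can be settled after the data are seen, and the nominal p-value then loses its meaning.

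**Working it through.** **Inputs.** Protocol 10.1: 34 randomised, about 80% power, effect size 0.75, 2-sided paired t-test at 0.05, 10% dropout. SAP 2.9: 19 patients, at least 70% power, 1-sided. The documents give no SD, no within-patient correlation, no 1-sided alpha and no effect size for any exploratory endpoint.

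**Step 1: reproduce the plan's figures, to see which alpha they imply.** Let d be the mean difference divided by the SD of the within-patient difference. If 0.75 is standardised by the single-measurement SD with within-patient correlation r, then d = 0.75/√(2(1−r)). Assume r = 0, so d = 0.75/√2 = 0.530. Power comes from the noncentral t distribution with n−1 df and noncentrality d√n.

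- Protocol: 80% power at 2-sided 0.05 needs n = 30 (power 80.2%), and 30/0.9 = 33.3, rounded up to 34. This matches.
- SAP, n = 19: noncentrality 0.530 × √19 = 2.31. Power is 71.9% at 1-sided 0.05, 59.0% at 1-sided 0.025 and 59.0% at 2-sided 0.05. Only 1-sided 0.05 gives at least 70%.
- If instead d = 0.75 directly, 80% power needs only n = 16 (18 randomised), and 19 patients give 87.1% (2-sided) or 93.3% (1-sided). Neither stated figure is reproduced.
- At r = 0.3, 19 patients would give 74.3% even at 2-sided 0.05, but 30 completers would then give 91.8%, not about 80%. The two stated figures fit together at r = 0 and 1-sided alpha 0.05. This is an inference, since the SAP states no alpha.

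**Step 2: a true rise when the test looks for a decrease.** Take n = 19, df = 16 (19 minus intercept, sequence and baseline difference) and 1-sided alpha 0.05. The critical values are t(0.95, 16) = 1.746 and t(0.975, 16) = 2.120. The noncentrality is d√19, for example 0.53 × 4.359 = 2.31. The chance of declaring the rise is P(T < −1.746) for the 1-sided test and P(|T| > 2.120) for the 2-sided test.

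| True rise (SD of within-patient difference) | 1-sided test for a decrease | 2-sided 0.05 | 1-sided 0.05 in the correct direction |
|---|---|---|---|
| 0.53 | 5.6e-5 | 58.3% | 71.4% |
| 0.75 | 8.5e-7 | 86.6% | 93.1% |
| 1.0 | 2.7e-9 | 98.3% | 99.4% |

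With 18 df the 2-sided column becomes 58.9%, 87.1% and 98.4%. For smaller rises (18 df), the 1-sided test for a decrease gives 0.6% at 0.2 SD and 0.2% at 0.3 SD, against 13.1% and 23.6% for the 2-sided test. These effect sizes are illustrative: 0.53 and 0.75 derive from the HQ-CT assumption, and 1.0 is a round value.

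**Step 3: how a 1-sided p-value is obtained.** SAP 6.1 bases significance on Type III tests. Those are F tests and do not distinguish sign. The SAP does not say how they become 1-sided, so the direction cannot be recovered from the method description either.

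**The case against.** The strongest reply is that the SAP assigns no direction to any endpoint. On that view, using the same methods means the same REML model, covariates and contrasts, and a sensible analyst would test UAG upwards, as Protocol 3.2 expects. This stands as far as it goes. A reader might infer that the plan tests UAG in the wrong tail and that a real rise would give a p-value near 1. The text does not say so, and the figures in the middle of Step 2 hold only if the HQ-CT direction is carried over. But the reply leaves the direction to be chosen later, which is also a defect.

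A reader might also infer that metabolic worsening would be invisible. It would not. SAP 8 tabulates values and changes from baseline at each time point and plots AG and UAG. SAP 6.1 gives least-squares means with 95% confidence intervals and GLWL-01 versus placebo contrasts. SAP 7.3 gives shift tables for the laboratory parameters. The size and sign of a rise would be on the page, and only the significance test would fail to mark it.

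A third inference is that exploratory decreases are declared at twice the protocol's one-tail error rate (0.05 against 0.025, a different decision for |t| between 1.75 and 2.12). That depends on a 1-sided alpha of 0.05, which Step 1 supports but the SAP does not state.

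It is also fair to say that only UAG is expected to move opposite to HQ-CT. AG, and with it the ratio, should fall, so evidence of target engagement does not rest on UAG alone. The change is disclosed, and Protocol 10.3.1 allows exceptions and SAP changes, so this is not a hidden contradiction. Finally, the endpoints are exploratory and unadjusted for multiplicity (SAP 2.6).

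**Conclusion.** The point holds as a mismatch between rule and purpose. A 1-sided rule justified by primary-endpoint power is applied to ten endpoints with a non-directional objective, with neither direction nor alpha stated. If the HQ-CT direction is applied, a rise of 0.53 SD has a chance of about 6e-5 of being declared significant, against 58% at 2-sided 0.05. If it is not applied, the direction can be settled after unblinding. The figures rest on 19 patients with complete data, 16 df, an assumed 1-sided alpha of 0.05 and illustrative effect sizes.

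The consequence is moderate. It limits what the exploratory p-values for UAG and the metabolic measures can mean. It does not hide the estimates and does not touch the primary result. It is a cheap improvement to make before unblinding.

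**What to change.** In SAP 2.9 and SAP 6, limit 1-sided testing to the primary HQ-CT comparison and, if wanted, the secondary efficacy endpoints. In SAP 8, state that all ten exploratory endpoints keep the protocol's 2-sided 0.05 test, each with a 2-sided 95% confidence interval for the GLWL-01 minus placebo difference.

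This is a few sentences of SAP text before unblinding. The model fit is the same, and the Type III tests already cited are non-directional. The cost is lower power for an exploratory effect in the expected direction, for example 58% instead of 71% at 0.53 SD, on endpoints that do not decide the trial.

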## 9. PHARMACOKINETIC ANALYSES

Analyses of the pharmacokinetic (PK) parameters will be addressed in a separate PK-specific analysis plan.

To investigate the potential effect of GLWL-01 on QT interval prolongation, the changes from baseline in QTcF values versus the plasma GLWL-01 concentration will be plotted.

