9.5. Pharmacokinetics

9.5.1. Blood Sampling and Processing

For all patients, serial blood samples will be collected on Day 1 and Day 28 of Treatment Period 1 for the determination of plasma concentrations of GLWL-01. Sample collection time points are specified in the Schedule of Activities ([Section 2](#)). Times of sampling are intended as a guide and may be modified to accommodate clinical procedures. The actual date and time (24-hour clock time) of each sample collection will be recorded. The date and time of dosing on the days of PK sample collection will also be recorded. Instructions for the collection and handling of blood samples will be provided by the sponsor in a separate document.

A maximum of 2 samples may be collected at additional time points during the study if warranted and agreed upon between both the investigator and sponsor. For patients who discontinue early, a PK sample should be taken at the early termination visit.

Drug concentration information that may unblind the study will not be reported to investigative sites or blinded personnel until the study has been unblinded. Placebo samples are not planned to be assayed.

9.5.2. *Bioanalytical Method*

Plasma sample bioassays of GLWL-01 will be performed using validated procedures and methods at a laboratory approved by the sponsor. Placebo samples will be shipped to the laboratory in order to maintain the blind, and are not planned to be assayed.

Bioanalytical samples collected to measure study drug concentration will be retained for a maximum of 1 year following last patient visit for the study.

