10.3.5. Pharmacokinetic/Pharmacodynamic Analyses

Plasma GLWL-01 PK parameters will be calculated using noncompartmental methods after single and multiple dose administration (on Day 1 and Day 28 of Treatment Period 1, respectively). Additional PK parameters may be calculated if deemed appropriate.

Pharmacokinetic parameters will be summarized by dose level using descriptive statistics. Mean and individual GLWL-01 plasma concentration-time curves will be represented graphically.

Accumulation will be estimated. Additional analyses will be performed as deemed necessary upon review of the data.

Pharmacokinetic data may be fit with a population PK model; and may be pooled with data from previous studies.

Pharmacodynamics of GLWL-01 will be based on plasma AG and potentially UAG measures. Raw and change from baseline values will be reported and summarized for AG and potentially UAG.

The PK/PD relationship of GLWL-01 with PD, efficacy, and/or safety measures may be explored.

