## **2.3. Definition of Study Time Points**

For the summarization of demographic and background characteristics, the value of an endpoint will be the last measurement taken prior to the first dose of double-blind study drug during Treatment Period 1 on Study Day 14.

Baseline values will be determined separately for each treatment phase. The baseline values for each double-blind treatment phase will include the last measurements taken prior to or on the date of the first dose of the double-blind study drug, on Study Day 14 and Study Day 84, unless the time of the assessment/event was after the time the dose was administered. Treatment phase day will be defined separately for each treatment phase as

Treatment phase day = Visit Date – Date of 1st dose of double-blind study drug.

Therefore, Study Day 14 and Study Day 84 will be considered Treatment Phase Day 0 (i.e. Baseline) for Treatment Phase 1 and Treatment Phase 2, respectively. Similarly, Study Day 42 and Study Day 112 will be considered Treatment Phase Day 28 for Treatment Phase 1 and Treatment Phase 2, respectively.

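### The concentration–QTcF plot in SAP section 9 states no placebo reference, so a shift shared across patients with time after dose could mimic or mask a drug effect; overlaying placebo ECGs already scheduled is a cheap improvement

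*SAP*

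**What the plan says.** SAP section 9 plans one output linking drug concentration to QTcF: "the changes from baseline in QTcF values versus the plasma GLWL-01 concentration will be plotted". Its stated purpose is to look for QT prolongation. The section mentions no placebo overlay, placebo subtraction, time matching or model. It also says that "Analyses of the pharmacokinetic (PK) parameters will be addressed in a separate PK-specific analysis plan". Protocol section 10.3.5 adds only that "The PK/PD relationship of GLWL-01 with PD, efficacy, and/or safety measures may be explored".

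The data behind the plot are set elsewhere:

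- **Concentrations.** Protocol section 9.5.1: "serial blood samples will be collected on Day 1 and Day 28 of Treatment Period 1" (Study Days 14 and 42), and "Placebo samples are not planned to be assayed". That section also allows an early-termination sample and up to 2 optional extra samples.
- **ECGs.** SAP section 7.5 places them "on Treatment Phase Day 0 (i.e. Baseline), Treatment Phase Day 7, and Treatment Phase Day 28 of each treatment phase", and adds: "Two-hour post-dose ECG assessments will also be made at Baseline of each treatment phase". The Schedule of Activities agrees, with 2-hour ECGs at Visits 3 and 8.
- **Baseline.** SAP section 2.3 takes the last value up to the first double-blind dose of each phase, "unless the time of the assessment/event was after the time the dose was administered". The 2-hour ECG is therefore post-baseline.

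**The concern.** The plot is meant to show whether QTcF rises with concentration. On Day 14, concentration and time since baseline rise together in every patient on drug. If QTcF drifts over those hours for reasons other than drug (time of day, food, site procedures), the drift appears at high concentration and looks like a drug effect. A downward drift could hide a real one. Placebo ECGs at the same nominal times show the drift directly. They are scheduled for every completer, but the SAP does not say that they enter the figure.

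The figure matters because SAP section 7 plans no statistical analyses of safety endpoints, and Protocol section 7.7 admits patients on stable QT-prolonging medication. Readers will look to this plot for an exposure-related QT signal.

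**Working it through.** The documents give no figure for this analysis, so there is none to reproduce. The check sets the schedule out and follows the algebra.

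**1. Who contributes concentrations.** Serial PK is in Period 1 only and placebo is not assayed, so it comes from GLWL-01-first patients. SAP section 2.9 anticipates 19 patients; at 1:1, 19 / 2 = 9.5, so 9 or 10. With the planned 34 it would be 17.

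**2. Which ECGs pair with a concentration in those patients.**

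| ECG in Period 1 | PK sample | QTcF change |
|---|---|---|
| Day 14, pre-dose | yes | zero by definition |
| Day 14, 2 h | yes (2 h) | drug effect plus any time-after-dose shift |
| Day 21 (phase Day 7) | none scheduled | not plotted |
| Day 42 (phase Day 28) | yes, but ECG time relative to dose not stated | depends on that time |

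That leaves about 2 informative pairs per patient, or 18 to 20 in all. Protocol section 3.2 gives a median time to peak of about 1 to 2 hours on Day 1 in the earlier study, so the 2-hour ECG falls near peak.

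**3. The algebra at 2 hours.** Let D be the drug effect, s1 and s2 the shared time-after-dose shifts in Periods 1 and 2, and e noise.

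- On drug, Period 1: change = D + s1 + e
- Placebo-first patients, Period 1: change = s1 + e
- The GLWL-01-first patient's own placebo phase, Period 2: change = s2 + e

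The planned plot shows D + s1. The difference from concurrent placebo has expectation D. The within-patient difference has expectation D + (s1 − s2), so it carries any period difference.

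**4. Illustration (assumed values).** With D = 0 and s1 = −10, −5, +5 or +10 msec, the mean 2-hour change is −10, −5, +5 or +10 msec. With D = +10 and s1 = −10, it is 0. With s1 = 0 there is no distortion.

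**5. Does spread in concentration between patients remove the problem?** A simulation with no drug effect used 9 patients, an SD of 8 msec for the QTcF change, log-scale concentration SD 0.4, and Day 42 concentration at 20% of peak with no shift there (all assumed). The same four shifts gave false slopes of about −8, −4, +4 and +8 msec per median peak concentration. As a check on the 20%: 10 hours of simple exponential decline from a 2-hour peak, at the 3 to 6 hour half-life in Protocol section 3.2, leaves 2^(−10/3) ≈ 10% to 2^(−10/6) ≈ 31%. Under these assumptions, the spread between patients does not remove the distortion.

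**6. Noise of the 2-hour mean (assumed single-ECG SD 6 to 9 msec, independent errors).** SD of a change = 6√2 to 9√2 = 8.5 to 12.7 msec.

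- On drug, n = 10: 8.5/√10 to 12.7/√10 = 2.7 to 4.0 msec
- Minus own placebo: √2 times that = 3.8 to 5.7 msec
- Minus 9 concurrent placebo-first patients: 8.5 to 12.7 times √(1/10 + 1/9) = 3.9 to 5.8 msec

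On these assumptions the concurrent reference costs about as much precision as the within-patient one and avoids the period difference.

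**7. Is the Visit 8 reference time-matched?** Protocol section 7.2.1 limits on-site dosing to Days 14 and 42, and the Schedule of Activities marks it only at Visits 3 and 5. The same schedule and SAP section 7.5 call for a 2-hour post-dose ECG at Visit 8. These passages conflict or leave the dose time at Visit 8 uncontrolled. The Period 1 reference does not depend on them.

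**The case against.** **The SAP may only be brief.** One sentence does not exclude placebo points. Figure formats sit in a companion document, added exploratory analyses need no amendment (SAP section 1.1), and a separate PK plan exists. This stands in part: the point is under-specification, not proof that the final figure will lack placebo. But the PK plan is described as covering PK parameters, the Protocol's exposure–safety line is optional, and nothing available supplies the reference.

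**Placebo-referenced QTcF output exists.** SAP section 7.5 counts patients over QTcF and change thresholds, and SAP section 2.8 and Protocol section 10.3.4 provide for summaries by treatment. This stands: a reader might infer that the drug–placebo QTcF comparison rests on the plot alone, and it does not. Those counts do not use concentration, however.

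**The plot is not uninformative.** A reader might infer that it cannot separate drug from time at all. That goes too far. Patients differ in concentration at the same 2-hour time. If the Day 42 ECG is pre-dose, as the ECG-before-PK order in the schedule would allow, that pair has drug on board at about the baseline's time relative to dosing. Early-termination or optional samples could also add Period 2 points.

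**No false-alarm rate follows.** A reader might want one. It would need assumed SDs and shifts, and a test that the SAP does not plan.

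**Subtracting each patient's own placebo phase is not a clean cure.** This stands. For these patients it is Period 1 drug minus Period 2 placebo.

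**Conclusion.** The point holds as a gap in a descriptive figure. As written, the plot states no placebo reference, draws essentially on 9 to 10 of 19 patients (1:1 assumed), and passes any shared time-after-dose shift one for one into its near-peak Day 14 points. The pass-through is algebra; whether a shift exists, and how large, is not in the documents. The clearest exposure is at 2 hours; Day 42 is affected only if its ECG is taken at a different time relative to dosing from the baseline. No endpoint, test or stopping rule is touched. This is a cheap improvement, not a major defect.

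**What to change.** In SAP section 9:

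1. Overlay placebo-phase QTcF changes at concentration zero, marked by nominal time (2 hours, phase Day 7, phase Day 28) and by period. Name the Period 1 placebo-first patients as the main reference.
2. State how many patients and ECG–concentration pairs contribute, and that serial PK exists only for the GLWL-01-first patients.
3. Optionally, add a supportive plot of within-patient placebo-corrected change. Its footnote should say that each point is essentially Period 1 drug minus Period 2 placebo, so it carries any period difference, and that its standard error is about √2 larger if the two phase changes are independent.
4. Before Visit 8 is used as a time-matched reference, reconcile the on-site dosing text in Protocol section 7.2.1 and the Schedule of Activities with the 2-hour post-dose ECG at Visit 8 in that schedule and SAP section 7.5.

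Items 1 to 3 cost SAP wording, an overlay and at most one extra figure, all from data already scheduled. No new visit, sample or assay is needed. Item 4 is a clarification of the documents.
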